7.2.3 Restrictions

7.2.3.1 Restrictions regarding concomitant treatment

Concomitant medications, or therapy to provide adequate supportive care, may be given as clinically necessary.

Additional experimental immunosuppressant treatment and/or standard immunotherapy is not allowed concomitantly with the administration of study treatment.

7.2.3.2 Restrictions on diet and life style

Subjects should be advised there are no dietary restrictions.

To prevent skin related adverse events it is recommended to avoid intense irradiation with UV light and harsh detergents. In addition, subjects will be advised not to have sexual intercourse during the nights in which they applied vaginal suppositories and to perform a vaginal douche in the morning. Subjects will be instructed to suspend the application of vaginal suppositories during the first 3 days of their menses

7.2.3.3 Women of Child-Bearing Potential and Pregnancy Prevention

Subjects who are not of childbearing potential due to being postmenopausal (1 year without menstruation) or surgical sterilisation (bilateral oophorectomy and/or tubal ligation) do not need to use contraception to be eligible for the trial.

All other subjects are considered to have childbearing potential and must use adequate contraception throughout the trial (from screening until end of trial participation).

Acceptable methods of contraception include surgical sterilisation and double barrier method, and must be in accordance with local regulations where applicable. Double barrier method of contraception is defined as two barrier methods used simultaneously each time the subject has intercourse. Accepted barrier methods include diaphragm, female condom, cervical cap, male condom and intrauterine device (IUD) (the diaphragm and cervical cap must be used in conjunction with spermicidal jelly/cream). Those using hormonal contraceptives, or with partners using hormonal contraceptives, must also be using an additional approved method of contraception (as described above). Partner vasectomy, natural "rhythm" and spermicidal jelly/cream are not acceptable methods of contraception.

HIC#: 1603017415 Protocol version 11.0

Women who become pregnant while participating in the study must discontinue study medication immediately. The pregnancy must be reported following procedures detailed in section 12.10.2.

7.3 Treatment compliance

The study medication will be given in accordance with the protocol and the instructions of the investigator.

The appropriate number of imiquimod suppositories for the first 8 weeks of imiquimod treatment course will be provided to subjects to be self-administered at home. At week 8 follow up visit, the appropriate number of imiquimod suppositories for weeks 9-16 imiquimod treatment course will be provided to subjects. Subjects will be asked to bring the remaining study medication at each follow-up visit (weeks 8, 16) to the investigator site for a compliance check. The remaining suppositories will be counted by the investigator/site staff and recorded at the investigator site. Discrepancies between the number of suppositories remaining and the calculated number the subjects should have used must be documented and explained. At the end of the 16-week period, any remaining medication will be collected.

The investigator can withdraw a subject from the study in the event of serious and persistent non-compliance which jeopardizes the subject's safety or render study results for this subject uninterpretable.

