samples (may be drawn after randomization but must be drawn prior to treatment), endocervical specimen to be sent to Yale Pathology for high-risk HPV DNA testing (if high-risk HPV DNA results are already available, this testing may not have to be repeated) and a second endocervical cytobrush specimen for translational research purposes. Blood samples will be collected in sodium heparin tubes with about 28 cc collected each time as follows: 7 cc in each of 3 green top tubes and 7 cc in 1 EDTA/purple top tube (see follow up visits below). Endocervical specimen for high-risk HPV DNA test to be performed by Yale Pathology will be submitted in usual fashion as a SurePath specimen. Endocervical cytobrush sample for study purposes will be collected into a 50ml conical tubes containing PBS using sterile techniques and will be stored on ice until picked up by a laboratory personnel. Once all eligibility has been met the subject will be randomized to one of three arms.

Additional components of visit outline by study group:

- (1) Control group: Observation at specified study timepoints.
- (2) Imiquimod only: At the baseline visit, this group will receive instruction on imiquimod self application (16 week course) using a 6.25 mg vaginal suppository, storage of medication, possible side effects. Subjects will be provided a diary and case report form to record vaginal suppository application and side effects will be recorded per NCI Common Terminology Criteria for Adverse Events (CTCAE 4.0). Imiquimod self-application regimen will be similar to one previously described²⁴ and is as follows:
- Treatment weeks 1 and 2: Subjects apply one vaginal suppository per week
- Treatment weeks 3 and 4: Subjects apply two vaginal suppositories per week
- Treatment weeks 5 to 16: Subjects apply three vaginal suppositories per week

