8.0 TREATMENT MODIFICATIONS: 9-valent HPV Vaccine

8.1 Dose reduction levels

8.1.1 Dose reduction for 9-valent HPV Vaccine

As the 9-valent HPV vaccine is not a continuous use medication, dose reduction will not be applied in the setting of treatment related toxicities. Subjects experiencing allergic reactions as described in table below will not receive additional doses of the HPV vaccine per FDA and CDC guidelines. Subjects experiencing local, self-limited site reactions will be eligible to receive additional doses of the vaccine.

Table 4: Discontinuation of HPV vaccine

AE type and CTCAE Grade	Action	Dose reduction scheme
Events related to study drug: Grade 3: • Anaphylaxis: Symptomatic bronchospasm, with or without urticaria; parenteral intervention indicated; allergy-related edema/angioedema; hypotension • Any drug related AE Grade ≥3	Treat adverse event or provide symptomatic relief if treatment not available. Discontinue or resume HPV vaccination protocol as noted in next column.	For anaphylactoid reaction, discontinue additional HPV vaccine administration. For all other Grade 3 AE, if subject has not recovered to Grade ≤2 or baseline¹ within 21 days, discontinue additional HPV vaccine administration. The decision to continue with additional HPV vaccine doses following an AE Grade ≤2 or a
		Grade 3 AE that resolves within

HIC#: 1603017415 Protocol version 11.0

21 days will be made by the investigator.

Baseline is defined as the CTCAE (version 4) Grade at the start of treatment

In the event of any unrelated adverse events, the investigator may choose to delay HPV vaccine administration for up to 21 days, but no dose reduction should occur. If vaccine administration is delayed for more than 21 days, the decision to continue with vaccination and possibly with study will be made by the investigator.

8.2 Management of adverse events, concomitant therapy, restrictions and rescue treatment

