8.3 Vaccine compliance

The vaccine will be administered in accordance with the protocol and the instructions of a site investigator. The 9-valent HPV vaccine will be administered in the clinic by a clinic or study nurse based on study protocol.

The investigator can withdraw a subject from the study in the event of serious and persistent non-compliance with receiving the vaccine dose(s) which jeopardizes the subject's safety or render study results for this subject unacceptable.

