15.0 DATA ANALYSIS / STATISTICAL METHODS

The analyses and methods described in this section, for this randomized, Phase II, single-blinded, 3-arm clinical trial, apply to the primary, secondary, and exploratory/correlative objectives provided in Sections 1.1 to 1.3

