15.2 Analysis Set Definitions

- **full analysis set**—all randomized subjects
- safety analysis set—all subjects who have received at least one dose of any study drug, and/or have had any assessments at baseline or later that could be associated with an AE; analyzed by treatment received
- ITT analysis set—all randomized subjects with valid baseline measurements; analyzed by treatment assigned
- modified ITT analysis set—all randomized subjects with valid baseline measurements, receiving at least one dose of any study drug, and have at least one valid post-baseline measurement of outcome; analyzed by treatment assigned

HIC#: 1603017415 Protocol version 11.0

- modified ITT completers analysis set—all randomized subjects who receive at least one dose of
 any study drug and have complete and valid post-baseline assessments of outcome; analyzed by
 treatment assigned
- **per protocol analysis set**—all randomized subjects who receive all doses of their assigned study drug, have complete and valid post-baseline assessments of outcome, and have no protocol deviations (e.g. dose modification, assessment outside of time window, non-compliance)

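### Non-compliance or vaccine delay can end study participation, in the active arms only, and nothing in the plan keeps these women for the week 20-24 biopsy

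*Combined protocol and SAP*

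**What the plan says.** Three rules let a compliance or scheduling problem end study participation and not only treatment.

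- **Section 7.3 (imiquimod):** "The investigator can withdraw a subject from the study in the event of serious and persistent non-compliance", qualified by "which jeopardizes the subject's safety or render study results for this subject uninterpretable".
- **Section 8.3 (vaccine):** the same power for "serious and persistent non-compliance with receiving the vaccine dose(s) which jeopardizes the subject's safety or render study results for this subject unacceptable".
- **Section 8.1.1 (vaccine):** in a paragraph on unrelated adverse events, if vaccination is delayed by more than 21 days, "the decision to continue with vaccination and possibly with study will be made by the investigator".

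Section 6.2.1 describes the first arm as "Control group: Observation at specified study timepoints". It has no drug or vaccine to comply with.

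Section 15.0 describes the trial as "for this randomized, Phase II, single-blinded, 3-arm clinical trial". Sections 5.1 and 6.2 describe blinding only for the pathologists, and in 6.2.1 the investigator prescribes the study drug.

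The only post-baseline biopsy required of every woman is at weeks 20-24 (6.2.2). Biopsies at weeks 8 and 16 are taken only if clinically indicated.

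Section 15.5 puts the primary analysis on the modified ITT set. Under 15.2 its members must "have at least one valid post-baseline measurement of outcome; analyzed by treatment assigned". Section 15.1 rules out imputation.

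The evaluability paragraph at the end of 15.8 differs. It eliminates only ineligible subjects, and it keeps women whose efficacy cannot be determined as a category of unknowns that is reflected in the response rate.

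**The concern.** An analysis by assigned treatment treats poor compliance as part of what the treatment achieves. A woman who took few suppositories still has an interpretable week 20-24 histology, and 15.2 already defines a per-protocol set that leaves out non-compliers. A results-based ground for taking her off study therefore gains nothing for the primary analysis and loses her outcome.

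The loss is one-sided by design. 7.3 acts in both active arms, 8.3 and 8.1.1 act only in the vaccine arm, and none acts in the control arm. The judgement is made with the arm known. The week 8 compliance check falls at the same visit as a colposcopy, so lesion appearance may be known too. If the women who leave are less likely to regress than those who stay, p1 and p2 are overstated relative to p0 in the co-primary comparisons.

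**Working it through.** **Inputs from the plan.** Control regression 28% and planned difference 35 points, so 63% in an active arm (15.8). One-sided Fisher's exact test at 0.025 per comparison (15.5). 38 evaluable and 46 randomised per arm, with 20% dropout (15.8).

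**Assumptions, not in the plan.** The share f (or number k) withdrawn from an active arm, and the regression rate pn of those withdrawn. Control women are all observed and analysed. Withdrawn women are excluded, as 15.1 and 15.2 imply.

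**Reproducing the plan's figures.** Exact enumeration over two binomials with n = 38 per arm gives a rejection probability of 0.0147 at difference 0 and 0.8269 at difference 0.35. Both match the operating-characteristics table in 15.8.

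**Bias when the treatment works.** Compliers regress at 63%. The as-assigned rate is (1 − f) × 0.63 + f × pn, while the observed rate stays at 0.63.

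| f | pn | As-assigned rate | Overstatement |
|---|---|---|---|
| 10% | 28% | 0.9 × 0.63 + 0.1 × 0.28 = 59.5% | 3.5 points |
| 20% | 28% | 0.8 × 0.63 + 0.2 × 0.28 = 56.0% | 7.0 points |
| 10% | 0% | 0.9 × 0.63 = 56.7% | 6.3 points |
| 20% | 0% | 0.8 × 0.63 = 50.4% | 12.6 points |

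**Same women kept in the denominator as not regressed** (one reading of 15.8), with pn = 28%. The observed rate is (1 − f) × 0.63, which is 56.7% against 59.5% (−2.8 points) or 50.4% against 56.0% (−5.6 points). The direction of the error depends on which section governs.

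**Type I error under no effect.** The true rate is 28% in both arms, with 46 controls and 46 − k active women analysed. The retained active women regress at (46 × 0.28 − k × pn)/(46 − k). For k = 5 this is (12.88 − 0.70)/41 = 29.7% at pn = 14%, and 12.88/41 = 31.4% at pn = 0.

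| k | pn = 28% | pn = 14% | pn = 0 |
|---|---|---|---|
| 0 | 0.0145 | 0.0145 | 0.0145 |
| 4 | 0.0137 | 0.0192 | 0.0263 |
| 5 | 0.0165 | 0.0257 | 0.0385 |
| 6 | 0.0135 | 0.0233 | 0.0380 |
| 7 | 0.0123 | 0.0228 | 0.0397 |
| 8 | 0.0163 | 0.0331 | 0.0608 |
| 9 | 0.0132 | 0.0302 | 0.0605 |

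Across k = 1 to 9, the error stays between 0.012 and 0.017 when withdrawal is unrelated to outcome (pn = 28%). At pn = 14% it exceeds 0.025 only for k = 5, 8 and 9. The column is not monotone because the test is discrete.

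**The case against.** Four points on the other side have force.

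1. **The threshold is high.** 7.3 and 8.3 need non-compliance that is both serious and persistent, plus a safety or interpretability consequence, and they permit withdrawal without requiring it. The 8.1.1 rule sits in a paragraph on unrelated adverse events, and only previously unvaccinated women have a second vaccine dose. Missed imiquimod doses can be made up the next day. Few women may be affected, and 20% withdrawal under these rules alone would use up the whole planned dropout. This limits the size of the problem but does not remove it.

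2. **Section 15.8 may keep these women in.** If unknowns stay in the denominator, active rates fall rather than rise. That stands as a reading, but it conflicts with 15.1 and 15.2, and 15.5 names the modified ITT set for the primary test. Under either reading the actual histology is missing.

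3. **Under no effect, missing doses of an inactive drug cannot lower regression.** This is correct. Type I inflation needs withdrawal selected on prognosis. The rules leave room for that, but nothing in the documents shows it would happen.

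4. **Other exits exist.** Worsening disease takes women off study in every arm. That rule is separate and not at issue here.

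A reader might also infer that women who stop imiquimod for local reactions are withdrawn under these rules. They are not: 7.1.1 and Table 2 interrupt, reduce or discontinue treatment and do not end study participation.

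**Conclusion.** The concern holds as a gap in the wording. Sections 7.3, 8.3 and 8.1.1 allow an arm-aware decision to end follow-up in the active arms only, and no section secures the week 20-24 biopsy for a woman so withdrawn. An occasional biopsy at week 8 or 16 might supply an outcome for some, but not the planned one.

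The size is conditional. If compliers regress at 63% and removed women at 28%, the active rate is overstated by 3.5 points at 10% withdrawal and 7 points at 20%. Under no effect, removing 5 of 46 women gives a one-sided error of 0.0257 if they regress at 14% and 0.0385 if none regress, against 0.0145 with no removals and an allotted 0.025.

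A reader might go further and conclude that both co-primary comparisons are biased toward efficacy or that type I error is inflated. The documents do not support that. They give no withdrawal rate and no evidence that non-compliant women regress less, and the sections disagree on whether such women leave the analysis. The change is still worth making, because the risk can be avoided by wording and the data could not later show that it was harmless.

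**What to change.** 1. In 7.3 and 8.3, delete the ground for study withdrawal that rests on uninterpretable or unacceptable results. In 8.1.1, delete the words that extend the decision to study participation. The parallel imiquimod rule in 7.1.1, on interruption beyond 21 days for unrelated events, already concerns the drug alone.
2. State that non-compliance with, or delay of, imiquimod or vaccine does not by itself end follow-up. The woman is still asked to attend the scheduled week 20-24 colposcopy and biopsy and is analysed as randomised. Non-compliance then affects only the per-protocol set.
3. Leave unchanged the safety ground in 7.3 and 8.3, the rules on when drug or vaccine stops, and the rules on worsening disease and pregnancy.
4. Reconcile 15.1 and 15.2 with the evaluability paragraph of 15.8, so that one rule says how a woman without an outcome enters the primary analysis. This is needed in any case, since some women will decline the visit.

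The cost is an amendment to the wording; the visit and biopsy are already planned for all subjects. The downside is that active-arm regression rates may look slightly lower.

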8.0 TREATMENT MODIFICATIONS: 9-valent HPV Vaccine

8.1 Dose reduction levels

8.1.1 Dose reduction for 9-valent HPV Vaccine

As the 9-valent HPV vaccine is not a continuous use medication, dose reduction will not be applied in the setting of treatment related toxicities. Subjects experiencing allergic reactions as described in table below will not receive additional doses of the HPV vaccine per FDA and CDC guidelines. Subjects experiencing local, self-limited site reactions will be eligible to receive additional doses of the vaccine.

Table 4: Discontinuation of HPV vaccine

AE type and CTCAE Grade	Action	Dose reduction scheme
Events related to study drug: Grade 3: • Anaphylaxis: Symptomatic bronchospasm, with or without urticaria; parenteral intervention indicated; allergy-related edema/angioedema; hypotension • Any drug related AE Grade ≥3	Treat adverse event or provide symptomatic relief if treatment not available. Discontinue or resume HPV vaccination protocol as noted in next column.	For anaphylactoid reaction, discontinue additional HPV vaccine administration. For all other Grade 3 AE, if subject has not recovered to Grade ≤2 or baseline¹ within 21 days, discontinue additional HPV vaccine administration. The decision to continue with additional HPV vaccine doses following an AE Grade ≤2 or a
		Grade 3 AE that resolves within

HIC#: 1603017415 Protocol version 11.0

21 days will be made by the investigator.

Baseline is defined as the CTCAE (version 4) Grade at the start of treatment

In the event of any unrelated adverse events, the investigator may choose to delay HPV vaccine administration for up to 21 days, but no dose reduction should occur. If vaccine administration is delayed for more than 21 days, the decision to continue with vaccination and possibly with study will be made by the investigator.

8.2 Management of adverse events, concomitant therapy, restrictions and rescue treatment

8.2.1 Rescue medication, emergency procedures, and additional treatment(s)

8.2.1.1 Rescue medication

Rescue medications to reverse the actions of 9-valent HPV vaccine are not available. Potential adverse events should be treated symptomatically. Common adverse events of vaccination with 9-valent HPV vaccine with specified management recommendations and/or requirements include local reactions with pain, swelling or erythema at injection site and occasionally headaches or syncope. Rare events include anaphylactoid/hypersensitivity reactions which should serve as contraindication to administration of additional doses of 9-valent HPV vaccine as described above. To improve tolerability and the probability of clinical benefit, subjects should receive prompt and appropriate supportive care at the first signs of symptoms. Suggested treatments for AEs are described below.

8.2.1.2 Concomitant treatment(s)

Concomitant medications or therapy to provide adequate supportive care may be given as clinically necessary.

All concomitant therapy, including anaesthetic agents, vitamins, homeopathic/herbal remedies, nutritional supplements, must be recorded in the (e)CRF during the screening and treatment period, starting from the date of signature of informed consent, and ending at the EOT visit. After the EOT visit, only concomitant therapy indicated for treatment of an AE has to be reported.

If vaccination is delayed by more than 21 days, the decision to continue will be made by the investigator.

8.2.1.3 Emergency procedures

Careful management and assessment of all subjects with syncope should be performed to prevent serious secondary injuries (skull fracture, cerebral haemorrhage). Procedures will be in place to avoid injuries from falling and to restore cerebral perfusion if syncope occurs.

Subjects who develop anaphylactoid/hypersensitivity symptoms (symptomatic bronchospasm with or without urticarial, angioedema, hypotension) should receive immediate treatment including epinephrine 1:1000. If anaphylactoid/hypersensitivity reaction to 9-valent HPV is suspected, additional doses of the vaccine should be discontinued.

HIC#: 1603017415 Protocol version 11.0

8.2.2 Management of expected adverse events

Local injection site and headache adverse events are the most common side-effects associated with administration of 9-valent HPV vaccine. Syncope and anaphylactoid/hypersensitivity reactions are less commonly reported. Treatment of these side-effects should be proactive and should be started as early as possible after onset of symptoms.

8.2.2.1 Management of local injection site adverse events following administration of 9-valent HPV vaccine

Local injection site adverse events including pain, erythema, or swelling can occur shortly after injection. Swelling and erythema have been noted to be increased in some subjects with successive doses. Although usually mild to moderate, local site reactions can cause significant discomfort (Table 8.2.2.1: 5).

Table 5: Grade specific treatment recommendations for local injection site reactions:

Severity	Description	Specific intervention
(CTCAE Grading)		
Injection site reactio	n	
Mild (Grade 1)	Tenderness with or without associated symptoms (e.g., warmth, erythema, itching)	Advise symptomatic treatment with acetaminophen or ibuprofen and local ice application
Moderate (Grade 2)	Pain; lipodystrophy; edema; phlebitis	Continue acetaminophen or ibuprofen; assess for signs of local infection and additional dermatologic findings. Addition of topical antibiotic or corticosteroid if clinically indicated
Severe (Grade 3)	Ulceration or necrosis; severe tissue damage; operative intervention indicated	See Grade 2; Consider oral or IV antibiotic as clinically indicated and institute wound care, including surgical consultation if needed
Life threatening (Grade 4)	Life-threatening consequences; urgent intervention indicated	See Grade 3
Localized edema		
Mild (Grade 1)	Localized to dependent areas, no disability or functional impairment	Avoid prolonged dependent positions
Moderate (Grade 2)	Moderate localized edema and intervention indicated; limiting instrumental ADL	See Grade 1
Severe (Grade 3)	Severe localized edema and intervention indicated; limiting self care ADL	See Grade 1

^{*} If despite optimal supportive care, reactions do not resolve to CTC AE Grade ≤ 2 within 21 days, administration of additional HPV vaccine doses must be permanently discontinued. The decision to continue with additional HPV vaccine doses following an AE Grade ≤ 2 or a Grade 3 AE that resolves within 14 days will be made by the investigator.

8.2.2.2 Management recommendations for headache AEs following administration of 9-valent HPV vaccine: Headaches can occasionally develop, although usually mild to moderate (Table 8.2.2.2: 6).

HIC#: 1603017415 Protocol version 11.0

Table 6: Grade specific treatment recommendations for 9-valent HPV vaccine-related headache

symptoms:

Severity (CTCAE Grading)	Description	Specific intervention
Headaches		
Mild (Grade 1)	Mild pain	Consider symptomatic treatment with acetaminophen or ibuprofen
Moderate (Grade 2)	Moderate pain; limiting instrumental ADL	See Grade 1
Severe (Grade 3)	Severe pain; limiting self care ADL	See Grade 1

^{*} If despite optimal supportive care, reactions do not resolve to CTC AE Grade ≤ 2 within 21 days, administration of additional HPV vaccine doses must be permanently discontinued. The decision to continue with additional HPV vaccine doses following an AE Grade ≤2 or a Grade 3 AE that resolves within 21 days will be made by the investigator.

8.2.2.3 Management recommendations for syncopal AEs following administration of 9-valent HPV vaccine: Syncopal events occur rarely with injectable vaccines and are typically reported in adolescents and young adults, occurring within 15 minutes of vaccination. Avoiding falls is imperative.

Table 7: Grade specific treatment recommendations for 9-valent HPV vaccine related syncopal events:

Severity	Description	Specific intervention
(CTCAE Grading)		
Presyncope / Syncop	e	
Mild (Grade 1)	-	
Moderate (Grade 2)	Presyncope present (e.g., near fainting)	Advise subject to sit down, check vitals, consider oral hydration
Severe (Grade 3)	Fainting; orthostatic collapse	Help subject to lie down and avoid fall, check vitals and EKG, consider IV hydration

^{*} If despite optimal supportive care, reactions does not resolve to CTC AE Grade ≤ 2 within 21 days, administration of additional HPV vaccine doses must be permanently discontinued. The decision to continue with additional HPV vaccine doses following an AE Grade ≤2 or a Grade 3 AE that resolves within 21 days will be made by the investigator.

8.2.2.4 Management recommendations for anaphylactoid/hypersensitivity reactions following administration of 9-valent HPV vaccine: A rare AE seen with 9-valent HPV vaccine that clinically may present with breathing difficulty, dizziness, hypotension, cyanosis and loss of consciousness.

HIC#: 1603017415 Protocol version 11.0

Table 8: Grade specific treatment recommendations for 9-valent HPV vaccine-related anaphylactoid/hypersensitivity reactions

Severity	Description	Specific intervention			
(CTCAE Grading)					
Anaphylaxis					
Mild (Grade 1)	-	-			
Moderate (Grade 2)	-	-			
Severe (Grade 3)	Symptomatic bronchospasm, with or without urticaria; parenteral intervention indicated; allergy-related edema/angioedema; hypotension	Administer epinephrine (1:1000) intramuscularly immediately; additional supportive therapy as indicated including IV fluids, hospitalization for observation and airway management			
Life threatening (Grade 4)	Life-threatening consequences; urgent intervention indicated	See Grade 3			

